### **9.1.1.1 Replacement policy**

Subjects will not be replaced on study. All treated subjects will contribute to the final analyses.

### **9.1.2 Withdrawal of informed consent**

Subjects may voluntarily withdraw consent to participate in the study for any reason at any time. Withdrawal of consent occurs only when a subject:

- Does not want to participate in the study anymore, and
- Does not allow further collection of personal data

In this situation, the investigator should make a reasonable effort (e.g. telephone, e-mail, letter) to understand the primary reason for the subject's decision to withdraw his/her consent and record this information.

Study treatment must be discontinued and no further assessments conducted, and the data that would have been collected at subsequent visits will be considered missing.

Further attempts to contact the subject are not allowed unless safety findings require communicating or follow-up.

All efforts should be made to complete the assessments prior to study withdrawal. A final evaluation at the time of the subject's study withdrawal should be made as detailed in [Table 8-1b](#) or [Table 8-2](#), as applicable.

Novartis will continue to keep and use collected study information (including any data resulting from the analysis of a subject's samples until the time of withdrawal) according to applicable law.

For US and Japan: All biological samples not yet analyzed at the time of withdrawal may still be used for further testing/analysis in accordance with the terms of this protocol and of the informed consent form.

For EU and RoW: All biological samples not yet analyzed at the time of withdrawal will no longer be used, unless permitted by applicable law. They will be stored according to applicable legal requirements.

### 9.1.3 Lost to follow-up

For subjects whose status is unclear because they fail to appear for study visits without stating an intention to discontinue or withdraw, the investigator must show "due diligence" by documenting in the source documents steps taken to contact the subject, e.g. dates of telephone calls, registered letters, etc. A subject should not be considered as lost to follow-up until due diligence has been completed or until the end of the study.

### 9.1.4 Early study termination by the sponsor

The study can be terminated by Novartis at any time.

Reasons for early termination:

- Unexpected, significant, or unacceptable safety risk to subjects enrolled in the study
- Decision based on recommendations from applicable board(s) after review of safety and efficacy data
- Discontinuation of study drug development

In taking the decision to terminate, Novartis will always consider subject welfare and safety. Should early termination be necessary due to safety reasons, subjects must be seen as soon as possible and treated as a prematurely withdrawn subject. The investigator may be informed of additional procedures to be followed in order to ensure that adequate consideration is given to the protection of the subject's interests. The investigator or Novartis depending on local regulation will be responsible for informing IRBs/IECs of the early termination of the trial.

## 9.2 Study completion and post-study treatment

Study completion is defined as when the end of study criteria are met or, in the event of an early study termination decision, the date of that decision.

### 9.2.1 End of Study

The end of study for Part 1 is defined as the earliest occurrence of one of the following:

- All subjects have discontinued study treatment and completed the safety follow-up, or have died, withdrawn consent or are lost to follow-up.
- Another clinical study or an alternative treatment option becomes available to continue the provision of capmatinib, and all subjects ongoing are transferred to that clinical study or alternative treatment option. For subjects who had received at least one dose of spartalizumab, all required safety assessments up to 150 days from the last dose of spartalizumab treatment must be completed and at least 2 post-baseline tumor assessments are obtained for the purpose of primary outcome measure completion before a transfer to another clinical study or alternative treatment option to continue capmatinib treatment may be initiated. Note: For subjects who transfer to another clinical study or an alternative treatment option to continue provision of study treatment, the follow-up for safety, tumor assessment and survival will not be performed.

At the end of the study, every effort will be made to continue provision of study treatment outside this study through an alternative setting to subjects who in the opinion of the Investigator are still deriving clinical benefit.

Details on the timing of the primary analysis and final reporting of data are provided in [Section 12](#).

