**Table 8-1b Assessment Schedule - Part 1 (Single Arm Run-in Part) – applicable upon approval of protocol amendment 01**

Period	Treatment					Post treatment follow-up*				
						Safety Follow-up				
	Visit Name	C3	C4	Subsequen t cycles	EOT	30 day	60 day	90 day	120 day	150 day
Days	Days	D1	D1	D1		-	-	-	-	-
Concomitant medications	X (up to 150 days from last dose of spartalizumab or 30 days from last dose of capmatinib whichever is longer or start of new anti-neoplastic therapy).									
Adverse Events	X (up to 150 days from last dose of spartalizumab or 30 days from last dose of capmatinib whichever is longer, after start of new anti-neoplastic therapy only suspected AEs will be collected). For SAE reporting please refer to Section 10 .									
Physical Examination	S	S	S	S						
Weight	X	X	X	X						
Vital signs	X	X	X	X						
Performance status	X	X	X	X						
Hematology	X	X	X	X						
Chemistry	X	X	X	X						
Urinanalysis	S (if clinically indicated)									
Coagulation	X (if clinically indicated)									
Serum pregnancy test (urine test allowed in safety FU)	S	S	S	S	S	S	S	S	S	S
Thyroid Stimulating Hormone (TSH)	At day 1 of every cycle up to 150 days after the last dose of spartalizumab, then as clinically indicated. or as clinically indicated in subjects who have never received spartalizumab treatment).									
Free T3 and Free T4	X (only if TSH is abnormal)									
Hepatitis testing	X (if clinically indicated)									
CT/MRI of chest, abdomen, and pelvis with i.v. contrast	X (every 8 weeks until at least 2 post-baseline assessment have been obtained then every 12 weeks thereafter)									

Final

Period	Treatment				EOT	Post treatment follow-up*				
	Visit Name	C3	C4	Subsequent cycles		Safety Follow-up				
Days	Days	D1	D1	D1		30 day	60 day	90 day	120 day	150 day
Brain CT/MRI with i.v. contrast				X (If positive at baseline, follow the same schedule as CT/MRI of chest, abdomen, and pelvis. Or if clinically indicated.)						
CT/MRI of other metastatic sites (e.g., neck, etc.) if suspected				X (If positive at baseline, follow the same schedule as CT/MRI of chest, abdomen, and pelvis. Or if clinically indicated.)						
Whole body bone scan				If clinically indicated						
Localized CT, MRI, or X-Ray				X (If positive at baseline, follow the same schedule as CT/MRI of chest, abdomen, and pelvis. Or if clinically indicated.)						

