### 8.3.1.2 Post-baseline imaging assessments

Imaging assessments as described in [Table 8-3](#) should be performed at the time points specified using the same imaging modality used at baseline, irrespective of study treatment interruption or actual dosing (see [Table 8-1b](#) or [Table 8-2](#)). Imaging assessments for response evaluation will be performed every 8 weeks (+/- 7 days) until at least 2 post-baseline imaging assessments have been acquired, then every 12 weeks thereafter until disease progression as determined by investigator assessment per RECIST 1.1 or until EOT, whichever occurs the earliest.

**Note:** Imaging assessments should be scheduled using the first dose of study treatment in Part 1 and the day of randomization for Part 2 as the reference date (not the date of the previous tumor assessment), and should be respected regardless of whether treatment with study treatment is temporarily withheld or unscheduled assessments performed.

Additional imaging assessments may be performed at any time during the study at the investigator's discretion to support the efficacy evaluations for a subject, as necessary.

Clinical suspicion of disease progression at any time requires a physical examination and imaging assessments to be performed promptly rather than waiting for the next scheduled imaging assessment.

Each lesion that is measured at baseline must be measured by the same method (either same imaging method or by photography, including a metric ruler) and when possible, by the same local radiologist/physician throughout the study so that the comparison is consistent. If an off-schedule imaging assessment is performed because progression is suspected, subsequent imaging assessments should be performed in accordance with the original imaging schedule.

Combined PET/CT may be used only if the CT is of similar diagnostic quality as a CT performed without PET, including the utilization of *iv* contrast media. At the discretion of the Investigators, FDG-PET scans may be performed to document disease progression per RECIST 1.1 ([Appendix 1](#)).

All complete responses (CRs) and partial responses (PRs) must be confirmed by a second assessment. If the second assessment is performed outside the normal window of scans, it should not be performed earlier than 4 weeks after the scan where the criteria for response were first met.

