## 12.4.1.1 Definition of primary endpoint(s) / estimand(s)

### Overall response rate (ORR)

ORR is defined as the proportion of subjects with a confirmed best overall response (BOR) of complete response (CR) and partial response (PR) as per investigator assessment according to RECIST 1.1 (see [Appendix 1](#)).

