#### **12.4.1.4 Handling of missing values/censoring/discontinuations**

##### **Part 1: Single Arm Run-in Part**

Subjects in the FAS with unknown best overall response (BOR) will be noted as such in the appropriate tables/listings and counted as non-responders in the ORR calculation.

If there is no baseline tumor assessment, all post-baseline overall lesion responses are expected to be ‘Unknown’. If no valid post-baseline tumor assessments are available, the best overall response must be “Unknown” unless progression or death is reported.

If any new anti-neoplastic therapy is taken while on study any subsequent assessments would be excluded from the BOR derivation.

Subjects without confirmed CR/PR, due to lack of subsequent tumor assessment after one CR/PR, will be considered as non-responders.

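### The end-of-study rule calls two post-baseline scans enough for the primary outcome, but does not make transfer wait for the confirmation that a response needs in order to count

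*Protocol*

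**What the plan says.** Protocol 9.2.1 (End of Study) sets two cumulative conditions before a subject who has had at least one dose of spartalizumab may be transferred to another source of capmatinib. First, "all required safety assessments up to 150 days from the last dose of spartalizumab treatment must be completed". Second, "at least 2 post-baseline tumor assessments are obtained for the purpose of primary outcome measure completion before a transfer to another clinical study". After transfer, "the follow-up for safety, tumor assessment and survival will not be performed".

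The primary variable is confirmed CR or PR (Protocol 2.1 and 12.4.1.1; SAP 1.2.1 and 2.5.1). Appendix 1 (16.1.3.1) requires two qualifying determinations at least 4 weeks apart. Protocol 8.3.1.2 states: "All complete responses (CRs) and partial responses (PRs) must be confirmed by a second assessment". It lets that second scan be off-schedule, provided that it is not done within 4 weeks of the first.

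The Part 1 schedule in Table 8-1b is "every 8 weeks until at least 2 post-baseline assessment have been obtained then every 12 weeks thereafter".

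Protocol 12.4.1.4 settles the unconfirmed case: "Subjects without confirmed CR/PR, due to lack of subsequent tumor assessment after one CR/PR, will be considered as non-responders". SAP 2.5.4 has the same rule.

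**The concern.** Section 9.2.1 gives completion of the primary outcome as the reason for asking for two scans, but two scans do not complete a confirmed-response endpoint in general. They do so when the first shows CR/PR and the second confirms it. With stable disease at the first scan and a first PR at the second, the two-scan condition is met and the endpoint is still open. The same holds for any subject whose first CR/PR is on the most recent scan, however many came before.

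Section 9.2.1 does not refer to 8.3.1.2, Table 8-1b schedules no confirmatory scan, and 8.3.1.2 sets an earliest time for the off-schedule scan but no deadline. A site could follow 9.2.1 and Table 8-1b and regard the outcome as complete. The subject's status in the ORR would then depend on when the alternative capmatinib supply became available.

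The responses at risk are late first responses. Amendment 1 explains that all available scans count regardless of spartalizumab discontinuation so that a delayed effect of the combination is not missed. It also lengthened the interval after two scans to 12 weeks, which lengthens the wait for the next scheduled scan.

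**Working it through.** **The plan's own figure.** The only ORR calculation is Table 12-3 (SAP Table 3-1): the probability of at least 17 responses in 30. Binomial tails at true ORR 55%, 60% and 67% are 0.5025, 0.7145 and 0.9165, against 50.2%, 71.5% and 91.7% stated. The exact interval for 17/30 is 37.4 to 74.5, as stated. The table reproduces, and this point does not change it.

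**Timing inputs.** Infusions every 28 days from day 1 (Protocol 6.1.3); transfer from the last infusion plus 150 days (9.2.1); scans at weeks 8, 16 and 28, that is days 57, 113 and 197 (Table 8-1b); confirmation no sooner than 28 days after the first response (8.3.1.2). The assumptions are infusions on schedule and the 8/16/28-week grid.

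Earliest transfer after *k* infusions = 1 + 28(*k* − 1) + 150.

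Earliest confirmation is 113 + 28 = day 141 for a first response at week 16, and 197 + 28 = day 225 for one at week 28.

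| Infusions | Last infusion | Transfer from | First response week 16 (confirm day 141) | First response week 28 (confirm day 225) |
|---|---|---|---|---|
| 1 | day 1 | day 151 | fits | transfer already allowed before the scan |
| 2 | day 29 | day 179 | fits | transfer already allowed before the scan |
| 3 | day 57 | day 207 | fits | does not fit: 225 − 207 = 18 days short |
| 4 | day 85 | day 235 | fits | fits: 235 − 225 = 10 days to spare |

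- *Week 16.* Even at the late edge of the ±7-day imaging window (day 120), confirmation is possible on day 148, before day 151. But the next *scheduled* scan (day 197) comes after the earliest transfer for one or two infusions, so the off-schedule scan is needed there. After three infusions, day 197 precedes day 207.
- *Week 28 after three infusions.* In dates: first infusion 02-Jun-2021, third on 28-Jul-2021 (the date enrollment was halted), week-28 scan 15-Dec-2021, transfer allowed from 25-Dec-2021, earliest confirmation 12-Jan-2022.

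**Who is exposed.** Amendment 1 (Study Update) reports 28 subjects treated with both drugs and 3 started on capmatinib alone. The 3 are outside the efficacy analysis (12.4.1.2), so the denominator is 28. On 06-Sep-2021, 19 of all 31 were still on treatment. Between 0 and 3 of those 19 could be capmatinib-only, so 19 − 3 = 16 to 19 combination subjects could still reach the transfer route.

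**Size.** One possible responder lost = 1/28 = 3.6 points. As an illustration, take 19/28, the first-line capmatinib monotherapy result in Protocol 1.1.1.2, as an assumed starting point:

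| Responders | ORR | Exact 95% CI |
|---|---|---|
| 19/28 | 67.9% | 47.6 to 84.1 |
| 18/28 | 64.3% | 44.1 to 81.4 |
| 17/28 | 60.7% | 40.6 to 78.5 |

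The range of 0 to 2 losses is an assumption. The documents do not say how many first responses come late, or how many subjects transfer.

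**The case against.** The strongest reply is that nothing is broken. Section 9.2.1 sets a floor of at least two scans and does not waive 8.3.1.2, which says every CR and PR must be confirmed and foresees an off-schedule scan. Both can be obeyed at once, and a response is lost only if 8.3.1.2 is not carried out before transfer. This stands against a reading that a reader might adopt, that the two sections contradict each other. They are unreconciled, not contradictory. It does not remove the gap: 9.2.1 is the section that says when a subject may leave, and it names a completion criterion that is not the endpoint's.

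A reader might also infer that stable disease at week 8 followed by PR at week 16 is lost under the rule. The documents do not support that, because a 4-week scan fits before the earliest transfer even after one infusion.

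A third inference would be that ORR is biased downward by a known amount. That is not supported either. A single PR is not an established response, and Appendix 1 says that confirmation guards against overstating the response rate. Counting unconfirmed responses as non-responses is prespecified in both documents. Protocol 1.1 expects rapid responses to targeted therapy, so late first responses may be few. The transfer route opens only if another source of capmatinib becomes available. Subjects past their second scan before the amendment took effect may not follow the 8/16/28-week grid.

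The consequence is also modest. Part 2 is cancelled, ORR is estimated without a test, and the SAP 2.5.5 waterfall plot would still show the shrinkage.

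**Conclusion.** The point holds as a gap in the completion rule. Section 9.2.1 can permit transfer before a first CR/PR on the latest scan is confirmed, and 12.4.1.4 and SAP 2.5.4 then count the subject as a non-responder. The clearest case is a first response at week 28 after three on-schedule infusions.

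Exposure is confined to subjects who transfer while on treatment. The number affected is unknown and may be zero. Any error goes one way, downward, by up to 3.6 points per subject; it is *up to* because some of these responses would not have been confirmed. It touches only the point estimate and its interval. This is a cheap improvement, not a threat to the validity of the analysis.

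**What to change.** In Protocol 9.2.1, keep the 150-day condition and extend the scan condition: at least two post-baseline assessments and, if the most recent is a first, unconfirmed CR or PR, completion before transfer of the confirmatory assessment that 8.3.1.2 already requires (at least 4 weeks later, off-schedule allowed).

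In the SAP, add one line to the ORR table with the number of subjects who are non-responders only because transfer or the end of the study came before confirmation. A reader can then see whether the gap mattered, including when the count is zero.

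The cost is one clause and one table line. No procedure is added, since 8.3.1.2 already calls for the scan. The downside is that transfer of a few subjects may be delayed by about 4 weeks.

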### **9.2.2 Post treatment follow-up**

After treatment discontinuation, all subjects will be followed for safety, as described in [Section 9.2.2.1](#).

Note: For subjects who transfer to another clinical study or an alternative treatment option to continue provision of study treatment, the follow-up for safety, tumor assessment and survival will not be performed.

#### **9.2.2.1 Safety follow-up**

All subjects must have safety evaluations for 150 days after the last dose of spartalizumab/placebo and 30 days after the last dose of capmatinib, whichever is longer. The subject will be followed via telephone call or onsite visit (if patient happens to be visiting the site) for the 30-, 60-, 90-, 120- and 150-day follow-up visits. Concomitant medications will be collected until the 30-day safety follow-up has been completed or the start of a new anti-neoplastic therapy, whichever occurs first.

For female subjects of child bearing potential, pregnancy tests will be performed as outlined in [Section 8.4.7](#).

The assessments required during safety follow-up are specified in [Table 8-1b](#) or [Table 8-2](#).

#### **9.2.2.2 Survival follow up**

Following the approval of protocol amendment 01, survival follow up will not be performed.

After completion of the safety follow-up, subjects will enter the survival follow-up period. Subjects will be contacted by telephone every 12 weeks to follow-up on their survival status. Any new anti-neoplastic therapies that have been started since the last contact date will also be collected during these phone calls. Date of progression on new antineoplastic therapies will also be collected.

## **10 Safety monitoring and reporting**

### **10.1 Definition of adverse events and reporting requirements**

#### **10.1.1 Adverse events**

An adverse event (AE) is any untoward medical occurrence (e.g. any unfavorable and unintended sign [including abnormal laboratory findings], symptom or disease) in a subject or clinical investigation subject after providing written informed consent for participation in the study. Therefore, an AE may or may not be temporally or causally associated with the use of a medicinal (investigational) product.

The investigator has the responsibility for managing the safety of individual subject and identifying adverse events.

Novartis qualified medical personnel will be readily available to advise on trial related medical questions or problems.

For subjects whose MET mutation status is unknown and who sign the molecular pre-screening ICF, AEs which occur after signature of this consent will only be captured if they meet the definition of serious as outlined in [Section 10.1.2](#) and are reported to be causally related with study procedures (e.g. an invasive procedure such as biopsy). Once the main study ICF is signed, all AEs per the descriptions below will be captured as adverse events.

Subjects whose MET mutation status is known will sign the main study ICF. AE collection starts at time of main study informed consent whether the subject is a screen failure or not.

The occurrence of adverse events must be sought by non-directive questioning of the subject at each visit during the study. Adverse events also may be detected when they are volunteered by the subject during or between visits or through physical examination findings, laboratory test findings, or other assessments.

Adverse events must be recorded under the signs, symptoms, or diagnosis associated with them, accompanied by the following information (as far as possible) (if the event is serious refer to [Section 10.1.2](#)):

1. CTCAE (version 5.0) grade. Grade 1 to 5 will be used to characterize the severity of the events.
2. its relationship to the study treatment. If the event is due to lack of efficacy or progression of underlying illness (i.e. progression of the study indication) the assessment of causality will usually be 'Not suspected.' The rationale for this guidance is that the symptoms of a lack of efficacy or progression of underlying illness are not caused by the trial drug, they happen in spite of its administration and/or both lack of efficacy and progression of underlying disease can only be evaluated meaningfully by an analysis of cohorts, not on a single subject
3. its duration (start and end dates) or if the event is ongoing, an outcome of not recovered/not resolved must be reported
4. whether it constitutes a SAE (see [Section 10.1.2](#) for definition of SAE) and which seriousness criteria have been met
5. action taken regarding with study treatment. All adverse events must be treated appropriately. Treatment may include one or more of the following:
  - Dose not changed
  - Dose Reduced/increased
  - Drug interrupted/withdrawn
6. its outcome

If the event worsens the event should be reported a second time on the eCRF noting the start date when the event worsens in toxicity. For grade 3 and 4 adverse events only, if improvement to a lower grade is determined a new entry for this event should be reported on the eCRF noting the start date when the event improved from having been grade 3 or grade 4.

Conditions that were already present at the time of informed consent should be recorded in medical history of the subject.

Adverse events (including lab abnormalities that constitute AEs) should be described using a diagnosis whenever possible, rather than individual underlying signs and symptoms.

Adverse event monitoring should be continued for at least 30 days after the last dose of capmatinib or 150 days after the last dose of spartalizumab/placebo, whichever is longer. If a patient starts a post treatment anti-neoplastic therapy sooner than the 30/150 days mentioned above, then only adverse events suspected to be related to study treatment should be collected.

Once an adverse event is detected, it must be followed until its resolution or until it is judged to be permanent (e.g. continuing at the end of the study), and assessment must be made at each visit (or more frequently, if necessary) of any changes in severity, the suspected relationship to the interventions required to treat it, and the outcome.

Progression of malignancy (including fatal outcomes), if documented by use of appropriate method (i.e. as per RECIST 1.1), should not be reported as a serious adverse event.

Adverse events separate from the progression of malignancy (i.e. deep vein thrombosis at the time of progression or hemoptysis concurrent with finding of disease progression) will be reported as per usual guidelines used for such events with proper attribution regarding relatedness to the drug.

Information about adverse drug reactions for the investigational drug can be found in the capmatinib and spartalizumab Investigator's Brochure.

Abnormal laboratory values or test results constitute adverse events only if they fulfill at least one of the following criteria:

- they induce clinical signs or symptoms
- they are considered clinically significant
- they require therapy

Clinically significant abnormal laboratory values or test results must be identified through a review of values outside of normal ranges/clinically notable ranges, significant changes from baseline or the previous visit, or values which are considered to be non-typical in subjects with the underlying disease.

